3.0 Outcome Measures/Endpoints

Standardized Clinical Measures

Toddler ASD Interview for Caregivers: Standard caregiver interview questions to assess for DSM-5 [39] [6]ASD criteria in toddlers. To be administered and ratings completed by the expert ASD specialist following the clinical interview. Additional ratings based on observation of the child throughout the evaluation will be completed by the expert ASD specialist.

Autism Diagnostic Observation Schedule, Second Edition (ADOS-2) [40]: The ADOS-2 is a semistructured standardized measure of social communication, play, and restricted and repetitive behaviors for individuals, ages 12 months and up, with varying developmental and language levels. Algorithm scores are compared with cutoff scores to yield a diagnostic classification (i.e., Autism, Autism Spectrum, or Non-spectrum; or Range of Concern for the Toddler Module). The comparison score allows for examination of an individual's overall level of ASD-related symptoms in relation to those of other same-aged children diagnosed with ASD who have similar language skills.

Mullen Scales of Early Learning (MSEL) [41]: The MSEL is a brief and reliable measure of cognitive ability in children from birth to 68 months of age, and includes five scales: Gross Motor, Visual Reception, Expressive Language, and Receptive Language. T-scores for each scale and an Early Learning Composite standard score are produced.

Vineland Adaptive Behavior Scales, Third Edition (VABS-3) [42]: The VABS-3 is a parent/caregiver interview that assesses a child's adaptive skills across the domains of Communication, Daily Living Skills, Socialization, Motor Skills, and Maladaptive Behavior.

Subdomain scaled scores, domain standard scores, and an Adaptive Behavior Composite standard score are derived from the measure.

Sensory Processing Assessment [43]: An abbreviated version of the Sensory Processing Assessment will be used to measure behavioral sensory responses to tactile, auditory, and/or visual information during play.

Biomarker Measures

An SR Research EyeLink Portable Duo remote eye-tracking system will be used to measure eye movements and pupil diameter. Four separate paradigms will be administered totaling 8-10 minutes in duration. Eye-tracking measures will include pupil dilation, percentage looking time, and latency to initiate saccadic eye movements.

Caregiver Report Measures

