12.0 Statistical Considerations

Statistical plan was developed in consultation with [name], PHD of IUSM Department of Biostatistics for NIH R21 proposal; for this funding mechanism, sample size was estimated at 120 participants; we are requesting IRB approval for a sample size of 300 participants to account for potential future funding for this project.

A sample of 120 children (with estimated distribution: ASD = 60, Non-ASD = 60) will provide the logistic regression models with 83% power for two-sided Wald tests to detect an odds ratio of 1.94, using alpha of 0.05. This calculation assumes that the proportion of ASD at a covariate mean value, versus 1 SD from the covariate mean value, equals 0.34 versus 0.50, for an odds ratio of 1.94. Most of the predictors are continuous variables. Under the worst case scenario for power, in which the predictor is binary and the prevalence of a predictor in one outcome category is 0.50 (e.g., without ASD), 60 in each group will provide 81% power to detect an odds ratio of 3.0 (i.e., when the predictor prevalence in the ASD outcome category is 0.75) using a two-sided Wald test and alpha of 0.05. No more than 5 independent variables will be allowed in the final models, according to the rule of thumb to have at least 10 persons per parameter (i.e., per each 1 *df* independent variable plus intercept) for the smallest sized category of the dependent variable.

Aim #1: Evaluate the diagnostic validity of the EE Hub model of ASD diagnosis in the communitybased primary care setting: Diagnostic validity will be measured by comparing agreement between the EE Hub and expert ASD-specialist on categorical diagnosis (ASD; non-ASD) to estimate diagnostic accuracy indices of sensitivity, specificity, positive predictive value, and negative predictive value. The kappa statistic for chance-corrected agreement, and its 95% confidence interval, will also be calculated.

Aim #2: Determine whether biobehavioral markers can reliably differentiate young children with and without ASD: Differences in metrics between children with and without ASD will be

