compared to validate potential biomarkers. Logistic regression with diagnosis as the dependent variable and eye-tracking measures as the independent variables will be used to estimate diagnostic accuracy indices (sensitivity, specificity, positive predictive value, and negative predictive value) at various cut-points on the continuous scale of eye-tracking measures, and to estimate the area under the receiver operator curve (AUROC) with the c-statistic. Bivariate logistic regression will be used to test each eye-tracking measure separately to determine its individual diagnostic efficacy; then multivariable logistic regression will be used, with eye-tracking measures simultaneously entered into the model, to test the joint effect of all eye-tracking measures on their combined diagnostic efficacy with respect to the diagnostic accuracy indices, as well as to determine which eye-tracking measures that do not contribute significantly to diagnostic efficacy will be deleted from the multivariable model.

Aim #3: Determine whether a combination of clinical and biobehavioral measures can be used to accurately predict ASD diagnostic outcome: We will evaluate the predictive efficacy of clinical measures and biobehavioral markers for accurate ASD diagnostic classification, and further determine whether a multivariable combination of clinical and biobehavioral measures may potentially provide a more promising method for ASD diagnostic classification of young children in the primary care setting. Classifier analysis for diagnostic outcome (ASD versus non-ASD as determined by the expert ASD-specialist) will be completed using the multivariable logistic regression procedure described above, except the model will contain clinical measures in addition to eye-tracking measures.

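### Aims 2 and 3 plan no internal validation of the multivariable models, so accuracy scored in the children used to fit and prune them will be too high on average; the five-variable cap does not correct this

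*Combined protocol and SAP*

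**What the plan says.** All references are to the combined protocol and SAP.

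- **Aim 2 (section 12.0).** After one-at-a-time models, all eye-tracking measures enter one logistic model "to test the joint effect of all eye-tracking measures on their combined diagnostic efficacy with respect to the diagnostic accuracy indices". The same step is to determine "which eye-tracking measures that do not contribute significantly to diagnostic efficacy will be deleted from the multivariable model". The indices are AUROC and, at various cut-points, sensitivity, specificity, PPV and NPV.
- **Aim 3 (section 12.0).** The same procedure is used, "except the model will contain clinical measures in addition to eye-tracking measures". The question is "whether a multivariable combination of clinical and biobehavioral measures may potentially provide a more promising method for ASD diagnostic classification".
- **Size limit (section 12.0).** "No more than 5 independent variables will be allowed in the final models", on a rule of ten persons per parameter in the smaller outcome group.
- **Sample (section 12.0).** 120 children, 60 with and 60 without ASD. For possible later funding, "we are requesting IRB approval for a sample size of 300 participants".
- **Candidates.** Aim 2 in section 2.0 names five eye-tracking measures: blink rate, pupil dilation, the pupillary light reflex, looking time and saccadic latency. Section 3.0 lists three: "Eye-tracking measures will include pupil dilation, percentage looking time, and latency to initiate saccadic eye movements". The clinical candidates for Aim 3 are not listed.

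Neither section 12.0 nor section 13.0 mentions a hold-out sample, cross-validation, bootstrap, shrinkage or optimism correction. The one reference to validating biomarkers describes a comparison of groups, not validation of a model.

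**The concern.** A regression model follows chance features of the sample it is fitted to, and deletion by significance favours measures that happened to look good there. Scoring the result in the same children therefore overstates, on average, what new children would show. Accuracy is the whole purpose of Aims 2 and 3, so the bias falls on the main result.

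In Aim 3, if apparent AUROCs are compared, the question of what eye-tracking adds to clinical measures is tilted toward the larger model. The clinical side can be expected to carry signal of its own: for the ADOS-2, "Algorithm scores are compared with cutoff scores to yield a diagnostic classification".

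**Working it through.** **1. The plan's own figures.** Odds ratio: (0.50/0.50)/(0.34/0.66) = 1.94, so b = ln 1.94 = 0.663. The Whittemore/Hsieh formula is n = (z_a + z_b·exp(−b²/4))²·(1+2pδ)/(p·b²), with δ = [1+(1+b²)exp(5b²/4)]/[1+exp(−b²/4)]. With p = 0.34 and n = 120, δ = 1.84 and z_b = 0.96, giving 83.2% power against the stated 83%. Cap: 60/10 = 6 parameters, that is 5 variables plus the intercept. Both reproduce and neither is disputed.

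**2. Design effect on the marker scale.** For a normal marker with equal variance in both groups, the log odds ratio per SD equals the mean difference in SDs, here about 0.66 SD. One such marker has AUROC Φ(0.663/√2) = 0.680. Two independent ones combined with ideal weights have Φ(0.663) = 0.746.

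**3. Simulation.** From the plan: 60/60, five or three eye-tracking candidates, final cap of 5. Assumed, because the documents do not say: independent normal markers, backward deletion at two-sided p<0.05, and the effect sizes other than 0.66 SD. For 300 children, 150/150 is assumed. The true AUROC of each fitted rule with weights w and mean differences μ is Φ(w·μ/√(2w·w)). There were 2000 replicates per setting.

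**4. Aim 2, five candidates, N = 120 (apparent / true AUROC).**

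| Real markers | All entered | After deletion, studies keeping a marker | Excess after deletion, all studies (none kept = 0.50) |
|---|---|---|---|
| two, 0.66 SD | 0.765 / 0.727 | 0.753 / 0.730 | +0.024 |
| two, 0.4 SD | 0.687 / 0.627 | 0.673 / 0.619 | +0.045 |
| two, 0.3 SD | not tabulated | 0.652 / 0.580 | +0.046 |
| none | 0.610 / 0.500 | 23% of studies keep a marker | +0.030 |

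With three candidates after deletion: 0.750 / 0.732 (0.66 SD) and 0.671 / 0.625 (0.4 SD). With all three entered, the excess is +0.02, +0.03 and +0.08 (0.66 SD, 0.4 SD, none).

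**5. N = 300, five candidates.** After deletion: +0.007, +0.016 and +0.026 (0.66, 0.4 and 0.3 SD). All entered: +0.015, +0.025 and +0.033; with no signal, +0.070.

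**6. Sensitivity, specificity, PPV and NPV.** At a fixed 0.5 probability cut with 50% ASD, after deletion, they are about 2, 4 and 5 points too high at N = 120 (0.66, 0.4 and 0.3 SD), and 0.6, 1.2 and 2 points at N = 300. Choosing the cut in the same data adds to this. With one design-effect marker among five candidates, sensitivity + specificity − 1 at the best cut is 0.326 against a true 0.221, an excess of 0.105.

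**7. Effect of the cap.** With one design-effect marker at N = 120, mean AUROC excess with and without the cap is 0.021 and 0.021 (5 candidates), 0.052 and 0.052 (15), and 0.069 and 0.070 (20). With five candidates the cap cannot bind. With 15 or 20 it binds in under 2% of studies.

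**8. Aim 3, combined against clinical-only, if apparent AUROCs are compared.** Assumed: three clinical measures (1.0 SD, 0.66 SD, one noise), five eye-tracking measures, N = 120, after deletion, 1500 replicates.

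| Eye-tracking signal | Apparent gain | True gain | Tilt |
|---|---|---|---|
| two, 0.66 SD | +0.061 | +0.042 | 0.019 |
| two, 0.4 SD | +0.027 | +0.005 | 0.022 |
| none | +0.005 | −0.005 | 0.010 |

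Over all settings tried (three or five eye-tracking measures, strongest clinical measure 1.0 or 1.5 SD) the tilt is 0.004 to 0.022, and 0.002 to 0.009 at N = 300. If five eye-tracking measures add nothing, the combined model still looks better in 21–23% of studies and truly is in 0–1%. Without deletion but within the cap (two clinical plus three eye-tracking), it looks better in 92% and is truly better in under 1%.

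**9. What is not affected.** A single marker with prespecified direction shows 0.679 against 0.680. Combined against eye-tracking alone is not reliably tilted (−0.021 to +0.009 after deletion), and there the combined model is truly better in every simulated study.

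**The case against.** Four points can be made in the plan's favour.

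- **Same-sample scoring is inferred.** The plan does not say which children are used for scoring and does not rule validation out. This is correct, but it names no other sample and no resampling, so following it as written produces the bias.
- **The bias is small at the only effect size the plan gives.** After deletion it is about 0.02 at N = 120, against a study-to-study SD of 0.046 for the apparent AUROC, and 28% of studies err the other way. At N = 300 it is 0.007 against 0.028. This stands, and the larger figures need weaker markers, no signal or the unpruned model. But the unpruned joint model is one the plan does assess, and the true marker strengths are unknown. Sampling error centres on the truth, whereas this error does not.
- **The Aim 3 comparison is not defined.** The plan names no comparison statistic and does not explicitly set out a clinical-only model. The clinical effects above are assumed, and the 92% figure is largely mechanical, since adding variables to an unpruned model rarely lowers apparent AUROC. The Aim 3 result is therefore conditional.
- **Resampling does not always reduce error for the pruned model.** This also stands and limits what the remedy can promise.

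None of these points changes the direction of the bias or makes the cap a correction for it.

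**Conclusion.** The concern holds and should be fixed, though it is not fatal. As written, the multivariable models in Aims 2 and 3 would report accuracy that is too high on average. At N = 120 and the design effect, with two real markers among five candidates, the AUROC excess is about 0.02 after deletion and 0.04 before. It reaches about 0.05 after deletion with 0.4 SD markers and 0.11 before deletion with no signal. At N = 300 it is smaller but not zero. If apparent AUROCs are compared in Aim 3, the tilt toward adding eye-tracking to clinical measures is modest, at most about 0.02 after deletion.

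The direction was the same in every Aim 2 setting and in every combined-against-clinical-only setting. The sizes rest on independent normal markers, equal groups, deletion at p<0.05 and assumed effects. The power calculation, single-marker AUROCs with prespecified direction, and Aim 1 are not affected.

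**What to change.** For each multivariable model in Aims 2 and 3, repeat entry, deletion and any cut-point choice inside bootstrap resamples or repeated nested cross-validation. Report optimism-corrected AUROC, sensitivity, specificity, PPV and NPV beside the apparent values, each clearly labelled. Base any Aim 3 comparison, above all combined against clinical-only, on corrected values from the same resamples. To program this, the deletion threshold and candidate measures must be fixed in advance, including whether measures dropped in Aim 2 re-enter Aim 3. It would also be useful to name in advance one model of at most five measures and report its corrected accuracy without deletion, because that is where the correction works best.

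**Cost.** SAP wording and some programming, with no new children or data. The reported figures become less favourable, and confidence intervals for corrected indices need further resampling.

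**Limits of the correction**, from a bootstrap check (300 studies per setting, 60 resamples each, five candidates, N = 120). Mean absolute AUROC error, apparent to corrected:

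- **Before deletion:** 0.044 to 0.037 (two 0.66 SD), 0.065 to 0.046 (two 0.4 SD), 0.105 to 0.044 (no signal). It helps throughout.
- **After deletion:** 0.041 to 0.042 at the design effect, where the mean moves from 0.751 to 0.721 against a true 0.729; 0.057 to 0.041 with two 0.4 SD markers; and worse with no signal, 0.027 to 0.054, when studies keeping no marker count as 0.50.
- **Aim 3, combined minus clinical-only, after deletion:** the mean gain is brought to +0.042 (true +0.042) and +0.003 (true +0.005) when eye-tracking is real, with no change in error. When it is null, the correction overshoots (−0.014, true −0.004) and error rises from 0.009 to 0.020, though the share of studies in which the combined model wrongly looks better falls from 22% to 11%.

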However, it is not yet known whether these biomarkers may accurately distinguish ASD from other children at high-risk for non-ASD neurodevelopmental disabilities. Further, it remains to be determined whether these eye-tracking indices can be successfully measured in the primary care setting. The proposed project builds on early evidence of potential ASD biomarkers by testing whether these data are able to be feasibly acquired in the community-based setting and if these indices can accurately classify children with ASD in a high-risk sample referred for neurodevelopmental evaluation.

Scientific Premise for Aim #3

Converging evidence from studies employing diverse (i.e., genetic, neuroimaging, behavioral) methodologies suggests that ASD is associated with multiple developmental pathways resulting in the emergence of a complex, heterogeneous phenotype. To assist in the diagnosis of ASD and account for this variability, several multivariate approaches using a single neuroimaging modality [33-35] or employing multiple imaging modalities [36] have been used for diagnostic classification. These methods have generally demonstrated positive results; however, as reviewed above, the utility of MRI in the context of early neurodevelopmental evaluation for ASD remains limited. Others have attempted to use multiple behavioral observational and parent/caregiverreport measures to classify ASD [37]. Despite clear group differences, classification of ASD (at 8 months) at the individual level using this approach was only moderately accurate. Recently, Lombardo and colleagues [38] combined neuroimaging and clinical measures to classify language outcomes in children with ASD. These authors showed that fMRI in combination with developmental, adaptive, and ASD symptom severity scores provided good specificity and sensitivity for future language outcome compared to any measure alone. The proposed project aims to adapt this approach by combining novel eye-tracking assays of ASD risk with standardized clinical measures in the context of community-based evaluation to predict diagnostic outcome.

2.0 **Objective(s)**

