The overall objective of this proposal is to test an innovative method of ASD diagnosis for young children in the primary care setting, which integrates clinical assessment by general pediatric providers with utilization of eye-tracking biomarkers to improve diagnostic accuracy. Our rationale for this project is that providing evidence for a novel, integrative model of ASD assessment in local communities has the potential to reduce barriers to care, resulting in earlier entry into evidence-based interventions, thereby improving outcomes and decreasing strain on the public health system. Three specific aims guide the proposed research:

Aim #1: Evaluate the diagnostic validity of the Early Evaluation (EE) Hub model of ASD diagnosis in the community-based primary care setting. A team at Indiana University School of Medicine has implemented a community-based early ASD evaluation program at primary-care practices across the state of Indiana. The EE Hubs will refer a consecutive sample of children, ages 14-48 months, for comprehensive expert ASD evaluation. Diagnostic validity will be measured by comparing agreement between the EE Hub and expert ASD-specialist on categorical diagnosis to estimate indices of diagnostic accuracy.

Aim #2: Determine whether biobehavioral markers can reliably differentiate young children with and without ASD in a high-risk community-referral sample. A series of eye-tracking measures (pupil dilation, pupillary light reflex, blink rate) will provide indirect measures of neuromodulator activity (i.e., norepinephrine, acetylcholine, and dopamine, respectively) and social (looking time) and non-social (saccadic latency) attentional processes. Differences in metrics between children with and without ASD will be compared to validate potential biomarkers.

Aim #3: Determine whether a combination of clinical and biobehavioral measures can be used to accurately predict ASD diagnostic outcome in a high-risk sample of young children evaluated in the primary care setting. We will evaluate the predictive efficacy of clinical measures and biobehavioral markers for accurate ASD diagnostic classification, and further determine whether a multimodal combination of clinical and biobehavioral measures may potentially provide a more promising method for ASD diagnostic classification in the primary care setting. Classifier analysis for diagnostic outcome will be completed.

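### Aim 3 leaves its clinical predictors unnamed and states no clinical-only model, AUROC difference or optimism correction for judging what eye-tracking adds

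*Combined protocol and SAP*

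**What the plan says.** **Outcome.** Section 12.0, Aim #3, fixes it in the words "Classifier analysis for diagnostic outcome (ASD versus non-ASD as determined by the expert ASD-specialist", that is, the specialist's call.

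**Model.** It is the Aim #2 multivariable logistic regression, "except the model will contain clinical measures in addition to eye-tracking measures". No clinical instrument is named. The Aim #2 procedure estimates accuracy indices and the c-statistic. It enters the eye-tracking measures together "to test the joint effect of all eye-tracking measures on their combined diagnostic efficacy", and it is also to "determine which eye-tracking measures that do not contribute significantly to diagnostic efficacy will be deleted from the multivariable model". Section 12.0 adds a size limit: "No more than 5 independent variables will be allowed in the final models".

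**Question.** Aim #3 will evaluate clinical measures and biomarkers, and then judge whether combining them is the better prospect for primary care. It gives no criterion for that judgement.

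**Purpose.** The Aim #3 premise in Section 1.0 speaks of "combining novel eye-tracking assays of ASD risk with standardized clinical measures in the context of community-based evaluation to predict diagnostic outcome". Section 2.0 describes a method that "integrates clinical assessment by general pediatric providers with utilization of eye-tracking biomarkers to improve diagnostic accuracy".

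**The concern.** Two gaps meet in one analysis.

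First, the predictors are open. Some candidates are collected by or under the specialist whose diagnosis is the outcome. If they feed that diagnosis and are then used to predict it, the model partly recovers its own ingredients. Its apparent accuracy would not carry over to a primary-care clinic that has only the Hub assessment.

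Second, the comparison is open. Whether eye-tracking adds to clinical assessment is a statement about the difference between two models. The plan describes the larger model and how it is trimmed, but not the smaller model, the difference, or an allowance for both being fitted and judged on the same children.

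At stake is the main claim of Aim 3, that the combined approach is better. As written, the predictors could be chosen after results are seen, and the apparent gain has a built-in tendency to be positive.

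**Working it through.** **1. The plan's own figures.**
- Odds ratio: (0.50/0.50)/(0.34/0.66) = 1.94.
- Power for a continuous predictor (Whittemore/Hsieh formula, N=120, P=0.34, b = ln 1.94 = 0.663, two-sided 0.05): δ = [1+(1+b²)exp(5b²/4)]/[1+exp(-b²/4)] = 1.84. Power = Φ{[√(NPb²/(1+2Pδ)) - 1.96]/exp(-b²/4)} = 83.2%, against 83% stated.
- Binary predictor, 60 per group, 0.50 versus 0.75: 81.6%, against 81% stated.
- Variable limit: 60/10 = 6 parameters, less the intercept = 5.

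These figures reproduce. They concern single-predictor Wald tests; none addresses a difference between two AUROCs.

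**2. Which clinical measures? The text side by side.**

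| Reading | Support |
|---|---|
| Reference-visit battery | The Aim #3 premise (Section 1.0) and the Section 3.0 list share one term for the measures. That list is the Toddler ASD Interview, ADOS-2, MSEL, VABS-3 and Sensory Processing Assessment. Section 7.0 places the testing at the research visit, by or under the specialist. The precedent cited in the premise used developmental, adaptive and symptom scores. |
| Hub assessment | Section 1.0 calls for tools used beside existing primary-care assessment and describes linking community evaluation with biomarkers. The premise sentence itself refers to community-based evaluation. Section 2.0 names general pediatric providers. Section 7.0 authorizes transfer of M-CHAT or M-CHAT-R/F, ASQ-3 and STAT scores, Hub diagnosis and certainty. |

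Section 6.0 masks the specialist to the Hub diagnosis. Nothing says the specialist diagnoses without the battery, and nothing says how much weight it carries.

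**3. Illustration of incorporation (all inputs assumed).** True status T ~ Bernoulli(0.5). Clinical scores A (overlapping) and H (independent) = d·T + N(0,1), with d = 1.2, 1.5 or 2.0 (true AUROC 0.80, 0.86, 0.92). The specialist's other information O = dO·T + N(0,1), with dO = d, 3 or 4. The diagnosis is positive when wA + (1-w)O exceeds [wd + (1-w)dO]/2, with w = 0.25, 0.5 or 0.75. That gives 27 scenarios.

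Inflation of A's AUROC above its true value:
- w = 0.25: -0.047 to +0.003
- w = 0.5: +0.01 to +0.09
- w = 0.75: +0.05 to +0.17
- accurate reference (dO = 3 or 4) with w = 0.25 to 0.5: -0.012 to +0.057

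The gap between A and H is wider, 0.01 to 0.31, but it mixes two effects. In the largest case, 0.308 = 0.173 inflation of A + 0.135 attenuation of H, with a reference only 78% accurate.

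**4. Effect on eye-tracking.** Add a real marker worth 0.8 SD. Its AUROC gain is 0.012 to 0.042 beside H and 0.001 to 0.039 beside A, lower in all 27 scenarios. Its adjusted coefficient, however, is larger beside A in 22 of 27. Section 7.0 collects eye-tracking at the same visit, and no masking of its output is stated. If the marker itself leaks into the diagnosis (d = 1.5, dO = 1.5, w = 0.5; marker weight 0, 0.1, 0.2), the gain beside A is 0.005, 0.014, 0.026. Beside H without leakage it is 0.021. The direction can reverse.

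**5. Optimism (assumed inputs).** Two Hub scores at d/√2 each, plus three markers unrelated to diagnosis, n=120, both models fitted and scored on the same data. The mean apparent AUROC gain is about 0.006 to 0.011 and positive in about 90 to 94% of simulated studies, while the true change is slightly negative. Over all 27 scenarios the mean reaches 0.021. At n=300 it is 0.002 to 0.009.

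**6. Precision of the proposed comparison.** Three real markers of 0.46 SD each (√3 × 0.46 ≈ 0.8 SD jointly): expected apparent difference 0.019 to 0.051, 95% half-width 0.023 to 0.058 at n=120 and 0.014 to 0.033 at n=300.

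**The case against.** **Hub measures may be what was meant.** Sections 1.0 and 2.0 support that, and it would largely remove the circularity. This stands: incorporation bias is conditional on the battery being used and on the specialist relying on it. A reader might infer that Aim 3 is circular as planned; the documents do not say so. They also do not rule it out, and one sentence would.

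**The comparator is partly there.** Aim #3 says it will evaluate clinical measures and biomarkers before combining them. Aim #2 supplies an eye-tracking-only model, a c-statistic and a joint test of the eye-tracking measures. This also stands. A reader might infer that clinical measures are never assessed alone; the text implies otherwise. What is absent is an explicit clinical-only fit, a stated difference between models, and any correction for optimism.

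**The sizes are assumed.** True. The 0.01 to 0.31 range in particular should not be read as bias in this study.

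**Overlap need not work against eye-tracking.** Correct; with unmasked output the net direction is unknown.

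**The variable limit is not breached.** Section 2.0 begins "A series of eye-tracking measures (pupil dilation, pupillary light reflex, blink rate" and adds looking time and saccadic latency, so five markers plus one clinical measure makes six. But the limit applies to final models, after deletion, so there is no contradiction. It is only a constraint on the fix.

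**Conclusion.** The point holds as a gap in specification that should be closed before analysis. Aim 3 does not say which clinical measures enter, does not specify the clinical-only model or the AUROC difference that its question requires, and does not correct for optimism.

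The absence of a specified comparison rests on the text alone. The incorporation part is conditional, and its size cannot be derived from the documents: about -0.01 to +0.06 above true AUROC with an accurate reference and weight 0.25 to 0.5, more if the battery dominates the diagnosis. The optimism part does not depend on which predictor set was meant, but its size (about 0.006 to 0.011 at n=120) also rests on assumed inputs. It is small in absolute terms, yet not negligible beside the 0.019 to 0.051 expected from real markers. The documents do not support a claim that bias has been shown or that eye-tracking is bound to be undervalued.

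**What to change.** In Section 12.0, Aim #3:

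1. Make the main analysis use a small pre-specified set of Hub-collected clinical measures, drawn from M-CHAT or M-CHAT-R/F, ASQ-3, STAT, Hub diagnosis and certainty. The sponsor chooses which of these, and which eye-tracking measures, enter, so that the final model meets the 5-variable limit.
2. Fit the clinical-only and the clinical plus eye-tracking models on the same children. Report the optimism-corrected AUROC difference with a bootstrap 95% CI, repeating any variable deletion inside the bootstrap.
3. Report any model using specialist-visit measures separately, labelled as subject to incorporation bias.

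**Cost.** This is SAP wording and some computing; sharing of the Hub data is already provided for in the authorization. The reported AUROC will probably be lower, and against an imperfect reference it may understate true accuracy (by 0.01 to 0.14 across the assumed scenarios). The difference will be imprecise at n=120, with a 95% half-width of about 0.02 to 0.06, so it should be read as an estimate. Hub measures are not fully independent of the reference either: M-CHAT-R/F is a route to referral (Section 4.0), and families know the Hub diagnosis when the specialist interviews them (Section 7.0).
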